7.4 Pregnancy

Female patients must be instructed to immediately inform the Investigator if they become pregnant during the study. The study treatment must immediately be stopped and the patient must be withdrawn from the study. Pregnancies occurring up to 3 months after the completion of the last treatment cycle must also be reported to the Investigator. The Investigator must report all pregnancies within 24 hours of knowledge to GSO. GSO will forward all pregnancy reports to the sponsor within 24 hours. The Investigator should counsel the patient; discuss the risks of continuing the pregnancy and the possible effects on the fetus. The patient should be monitored until the conclusion of the pregnancy.

Pregnancy occurring in the partner of a patient participating in the study should also be reported to the Investigator, the sponsor and the CRO. The partner should be counseled and followed as described above.

8 STATISTICAL METHODS

8.1 Trial Design and Hypotheses

This trial has been designed as a multi-center, open-label, two-stage phase II study in 3 separate gynaecological cancer cohorts, with an additional set of patients in the ovarian cohort randomized into two different treatment regimens.

Study data may be analyzed and reported to competent regulatory authorities when $\geq 75\%$ of patients have completed at least ≥ 2 cycles of treatment or discontinued from the study.

The primary objective is to determine the efficacy of selinexor in patients with advanced or metastatic gynaecological cancers as assessed by disease control rate (DCR). Disease control rate (DCR) is defined as complete response (CR) or partial response (PR) or stable disease (SD) for at least 12 weeks, assessed according to RECIST 1.1. The Simon's⁹⁷ two-stage optimal design will be used to address the primary trial objective, with the following hypothesis to be tested for DCR for each cohort:

H_0 : true disease control rate ≤ 0.25 versus H_1 : true disease control rate ≥ 0.50 .

Secondary objectives are:

[figure not shown]
- Determine the efficacy of selinexor in patients with advanced or metastatic gynaecological cancers using:
 - Objective response rate (ORR)
 - Progression-free survival (PFS)
 - Overall Survival (OS) including OS rates at 12 and 24 months
- Evaluate safety and tolerability of selinexor in patients with advanced or metastatic gynaecological cancers.
- Evaluate QoL for patients with advanced or metastatic gynaecological cancers treated with selinexor.

Patients enrolled into the second part of the study in the ovarian cohort will be randomized using a centralized randomization via IWRS. Randomization will be performed within the ovarian cohort and will not be specific to the study site.

Complete details of data analysis and presentation will be included in a statistical analysis plan (SAP) which will be finalized prior to database lock.

8.2 Sample Size Calculation

CCI

CCI

8.3 Evaluation Categories for Patients

8.3.1 Modified Intent-to-Treat Population

The treated population (mITT) will consist of all patients who receive at least one dose of study medication and have at least one post-baseline efficacy follow-up assessment, unless the patient discontinued treatment prior to the first assessment due to death, toxicity, or PD. This population will be used for primary analyses of efficacy.

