3.2 Registration of Patients

Patients to be enrolled are as follows:

- **Part 1:** As described in Section 8.2, approximately 21 evaluable patients will be enrolled in each cohort (Cohorts A, B, and C).
- **Part 2:** Approximately 32 additional patients (16 per schedule) with ovarian cancer will be enrolled in Cohort A. Each patient enrolled into this part of the study will be randomized into two treatment groups (Schedule 1 and Schedule 2) using centralized randomization via an interactive web-response system (IWRS). Randomization will be performed within the ovarian cohort and will not be specific to the study site.

Study drug administration may be delayed for toxicity as described in Section 6.3.

Patient eligibility will be confirmed by GSO once all screening procedures are completed. There will be no exceptions. Any questions should be addressed to GSO prior to registration. The eligibility check form/ Patient Registration Form will be sent from the site to GSO either by fax or email for evaluation. Upon confirmation of eligibility, GSO will assign a patient number and return the signed eligibility check form/ Patient Registration Form via fax or email to the site. The Patient Registration Form will confirm the treatment arm in which the patient will participate.

GSO
[contact]
UMS [contact]
Email: [contact]

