## **2. PATIENT POPULATIONS**

### **2.1. Population Definitions**

The following patient populations will be evaluated and used for presentation and analysis of the data:

- **Modified Intent-to-Treat (mITT) Population:** All patients who receive at least one dose of study medication, have measurable disease per RECIST at baseline, and have at least one post-baseline efficacy follow-up information. If the patient has measurable disease per RECIST at baseline, but discontinued treatment prior to the first assessment due to death, toxicity, or PD, they will still be included even if there is no post-baseline efficacy follow-up information. This population will be used for primary analyses of efficacy.
- **Per-Protocol (PP) Population:** All patients in the mITT population who are compliant with study assessments and who have no protocol violations that would compromise the assessment of efficacy. This population will be used for supportive inferences concerning efficacy. If there are major differences between the results in this population and those obtained in the mITT population, this will be taken into consideration in the decision to continue to later phase studies, or in the design of further studies.
- **GCIG Evaluable Population:** All patients in the ovarian cancer cohort (Cohort A) who receive at least one dose of study medication, have measurable disease per RECIST at baseline or a baseline CA-125 assessment, and have at least one post-baseline efficacy follow-up information (i.e. either a post-baseline scan or CA-125 assessment). If a patient discontinued treatment prior to the first assessment due to death, toxicity, or PD, they will still be included even if there is no post-baseline efficacy follow-up information. This population will be used for additional efficacy analyses specific to patients with ovarian cancer.
- **mITT Extended Population:** All patients who receive at least one dose of study medication and have at least one post-baseline efficacy follow-up information. If the patient discontinued treatment prior to the first assessment due to death, toxicity, or PD, they will still be included even if there is no post-baseline efficacy follow-up information. This population will be used for supportive efficacy analyses of select time-to-event endpoints (PFS and OS).

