#### 3.2. General Methods

All data listings that contain an evaluation date will contain a relative study day (Rel Day). Pre-treatment and on-treatment study days are numbered relative to the day of the first dose of study medication which is designated as Day 1. The preceding day is Day -1, the day before that is Day -2, etc. The last day of study medication is designated with an "L" (e.g., Day 14L). Post-treatment study days are numbered relative to the last dose and are designated as Day 1P, Day 2P, etc.

All output will be incorporated into Microsoft Word files, sorted and labeled according to the International Conference on Harmonization (ICH) recommendations, and formatted to the appropriate page size(s).

Tabulations will be produced for appropriate disposition, demographic, baseline, efficacy, and safety parameters. For categorical variables, summary tabulations of the number and percentage of patients within each category (with a category for missing data) of the parameter will be presented. For continuous variables, the number of patients, mean, median, standard deviation (Std Dev), minimum, and maximum values will be presented. Time-to-event data will be summarized using Kaplan-Meier (KM) methodology using 25th, 50th (median), and 75th percentiles with associated 2-sided 95% confidence interval (CI), as well as number and percentage of censored observations and events.

Data will be presented by study part, cohort, and schedule (Part 2 only) as follows:

- Part 1: Cohort A
- Part 1: Cohort B
- Part 1: Cohort C
- Part 2: Cohort A: Schedule 1
- Part 2: Cohort A: Schedule 2

Formal statistical hypothesis testing will be performed on the primary endpoint with all tests conducted at the one-sided 0.10 level of significance for Part 1 and at the two-sided 0.20 level of significance for Part 2. Summary statistics will be presented, as well as CIs on selected parameters, as described in the sections below.

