### **3.9. Withdrawals, Dropouts, Loss to Follow-up**

Patients will be free to discontinue treatment or withdraw from the study at any time, for any reason, or they may be withdrawn/ removed if necessary in order to protect their health. Patients who are withdrawn from the study will not be replaced.

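### The primary mITT set omits dosed patients with no post-baseline assessment unless they stopped for death, toxicity or PD; this raises the reported DCR or leaves it unchanged, and no visible analysis restores them.

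*Protocol*

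**What the plan says.** Protocol 8.3.1 defines the primary efficacy set as patients who received at least one dose and "have at least one post-baseline efficacy follow-up assessment, unless the patient discontinued treatment prior to the first assessment due to death, toxicity, or PD". SAP 2.1 keeps that rule ("and have at least one post-baseline efficacy follow-up information", with the same three exempt reasons) and adds measurable disease at baseline. SAP section 5 declares that addition.

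The other efficacy sets in SAP 2.1 do not bring these patients back:

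- The PP set lies inside mITT.
- The mITT Extended set drops the measurable-disease condition but keeps the early-leaver rule, and it serves PFS and OS only.
- The GCIG Evaluable set, used for the CA-125-based DCR in Cohort A, has the same rule.
- The Safety set takes every dosed patient but is assigned to safety endpoints.

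Protocol 8.4.1 plans no imputation of missing efficacy data. Protocol 8.4.3 and SAP 4.3.1 censor the duration of stable disease at time 0 when there is no post-baseline assessment. Protocol 5.5 lists removal reasons outside the three exempt ones, among them non-compliance, withdrawn consent, intercurrent illness and investigator discretion. Protocol 3.1 and SAP 1.2.1 keep disease evaluations going until PD after any stop other than PD, death or consent withdrawal. On replacement, SAP 3.9 states: "Patients who are withdrawn from the study will not be replaced".

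**The concern.** A dosed patient with no assessment, who left for a non-exempt reason, is absent from both numerator and denominator. Had she stayed in the denominator she could only have been a failure, because the plan has no way to credit control without an assessment. The omission therefore acts in one direction on the reported rate.

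What is at stake is a decision against a 25% null in about 21 patients per cohort, where one patient moves the estimate by about 2 points. The trial is open-label, and a poorly tolerated drug can lead to an early exit recorded either as toxicity or as withdrawn consent. The first label keeps the failure in the primary analysis; the second, if there was no assessment, removes it. In Part 2 the same rule is a post-randomisation exclusion in an unblinded comparison of two schedules.

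**Working it through.** **Inputs.** The hypotheses are "true disease control rate ≤ 0.25 versus H_1 : true disease control rate ≥ 0.50" (Protocol 8.1), under a Simon "two-stage optimal design will be used to address the primary trial objective". The test level is the "one-sided 0.10 level of significance for Part 1" (SAP 3.2). Protocol 3.2 gives about 21 evaluable patients per cohort. Protocol 8.5 gives 8 patients in stage 1, and its mention of 3 or more achievers implies continuing with at least 3. Power is redacted; 0.80 is assumed. No document gives the number of excluded patients, so every exclusion count below is also an assumption.

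**Reproducing the design.** With r1 = 2, the probability of rejecting H0 is

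P(reject; p) = sum over x = 3 to 8 of Bin(x; 8, p) × P(Y ≥ r + 1 − x), with Y ~ Bin(n − 8, p).

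An exhaustive search for the optimal design at one-sided alpha 0.10 and power 0.80 gives n1 = 8, r1 = 2, n = 21, r = 7, that is, reject with 8 or more of 21. Exact alpha is 0.0979 and power 0.811. At the same alpha, power 0.85 gives 11 then 24 patients and power 0.90 gives 10 then 27. The assumption of 0.80 is therefore supported by the match to 8 and 21.

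**Direction.** With x achievers among n mITT patients and k omitted patients who cannot be achievers, x/n ≥ x/(n + k). The two are equal only if x = 0 or k = 0.

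**Effect on the estimate at the cut-off.** Start from 8/21 = 38.1% and count the omitted patients as failures:

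| k | All treated | DCR |
|---|---|---|
| 1 | 8/22 | 36.4% |
| 2 | 8/23 | 34.8% |
| 3 | 8/24 | 33.3% |
| 4 | 8/25 | 32.0% |

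**Effect on the decision.** These cases take mITT as filled to 21 evaluable patients. Keep the stage 1 rule and put n = 22, r = 7 into the formula at p = 0.25: rejecting at 8 or more of 22 has alpha 0.115, above 0.10. So 8/21 meets the rule, while the same 8 achievers in 22 treated patients would not meet a rule held to 0.10.

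**Effect on type I error.** If the DCR among all treated is exactly 0.25 and a share d, all non-achievers, is left out, the rate in mITT is p = 0.25/(1 − d). Putting that into the 8/21 rule:

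| d | p in mITT | P(reject) |
|---|---|---|
| 0 | 0.250 | 0.098 |
| 5% | 0.263 | 0.124 |
| 10% | 0.278 | 0.157 |
| 20% | 0.3125 | 0.251 |

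The 5% row is about one patient per cohort (0.05 × 22 = 1.1).

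**Part 2.** There are 16 patients per schedule (Protocol 3.2), and SAP 3.2 and 4.3.1 specify Fisher's exact test at two-sided 0.20. With 8/16 v 4/16, p = 0.27. If two non-achievers in the first arm have no assessment and drop out, 8/14 v 4/16 gives p = 0.13. The result crosses 0.20 with no change in the number of achievers.

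**The case against.** The strongest reply is that few patients are affected. Stopping treatment does not remove anyone; having no assessment at all does. Because evaluations continue after most stops, a non-compliant patient or one stopped by the investigator before week 6 stays in mITT once she has a single assessment. A reader might infer that every early leaver outside the three exempt reasons disappears, and the documents do not support that. The likeliest early failures (death, toxicity, PD) are already kept. This stands and limits the size of the problem. It does not cover consent withdrawal, after which follow-up assessments cease (Protocol 5.5), or loss to follow-up and missed scans.

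A reader might also compare exact one-sided 90% lower bounds, 27.8% for 9/21 against 24.1% for 9/24, and conclude that three omissions reverse a cohort's result. That does not follow. The bound is a single-stage quantity and is not the decision rule: 8/21 has a bound of 23.6%, yet the re-derived design rejects there. Under the same stage 1 rule, rejecting at 9 or more of 24 has alpha 0.0885, so 9/24 still rejects. The example also needs 24 treated patients, which sits awkwardly with non-replacement. If 21 are treated and three are omitted, the comparison is 9/18 (bound 32.9%) against 9/21 (27.8%), both above 25%. The target of evaluable patients in Protocol 3.2 may allow extra enrolment, and the documents do not settle this.

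Three further points stand:

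- The upward direction is relative to an all-treated DCR with unassessed patients counted as failures. Against the unobservable true DCR it is not certain, since an omitted patient might have had control.
- The exploratory analyses (SAP 4.3.3) and the table list and shells are redacted, so the absence of an all-treated DCR can be asserted only for the visible text.
- SAP 4.1 tabulates population sizes and discontinuation reasons, so exclusions will be partly visible, though without their effect on DCR.

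**Conclusion.** The concern holds in a limited form. The mITT rule can make the reported DCR higher than, or equal to, the DCR in all treated patients, and never lower, provided unassessed patients count as not controlled. No analysis in the unredacted text shows the difference. The omitted group is probably small. Near the decision limit a small group is enough: one patient separates 8/21 (alpha 0.098) from 8/22 (alpha 0.115), and omitting 5% of treated patients already takes the type I error, referred to all treated patients, above the nominal 0.10.

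These figures rest on assumed exclusion counts, on power of 0.80, and on 21 patients being reached in mITT. They show sensitivity; they are not a forecast, and they do not show that any cohort's conclusion would change. The measurable-disease condition in the SAP is a separate exclusion that need not act in one direction, because patients without measurable disease can have disease control. It should not be mixed with this point. A supportive analysis should be added; the primary set need not change.

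**What to change.** Keep mITT as the primary set. Add a supportive DCR and ORR, for each Part 1 cohort and for the Part 2 comparison, in two sets:

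- (a) All dosed patients with measurable disease at baseline. This differs from the SAP's mITT only by the early-leaver rule, so it isolates that rule's effect.
- (b) All dosed patients (the Safety population), analysed by randomised schedule in Part 2.

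For DCR, count anyone without documented CR, PR or SD of at least 77 days (the SAP 4.3.1 threshold) as not controlled. For ORR, count anyone without documented CR or PR as a non-responder; the 77-day condition does not apply. List the number and reason for each mITT exclusion, by cohort and schedule.

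The cost is one extra table from data already collected. The supportive DCR in (a) will equal the mITT figure or lie slightly below it; in (b) it could move either way, because the measurable-disease restriction is lifted too. If no patient was omitted under the early-leaver rule, (a) will simply confirm the primary result.

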8.3.2 Per Protocol Population

The per-protocol population will consist of all patients who are compliant with study assessments and who have no protocol violations that would compromise the assessment of efficacy. Protocol violations will be determined independently of knowledge of response to therapy. This population will be used for supportive inferences concerning efficacy. If there are major differences between the results in this population and those obtained in the mITT population, this will be taken into consideration in the decision to continue to later phase studies, or in the design of further studies.

8.3.3 Safety Population

The safety population will consist of all patients who have received any amount of study medication.

8.4 Methods of Statistical Analysis

8.4.1 General Statistical Considerations

Tabulations will be produced for appropriate demographic, baseline, efficacy and safety parameters. For categorical variables, summary tabulations of the number and percentage of patients within each category (with a category for missing data) of the parameter will be presented, as well as two-sided 95% confidence intervals, unless otherwise stated. For continuous variables, the number of patients, mean, median, standard deviation, minimum, and maximum values will be presented. Time-to-event data will be summarized using Kaplan-Meier methodology using 25th, 50th (median), and 75th percentiles with associated 2-sided 95% confidence intervals, as well as percentage of censored observations.

No imputation of missing efficacy data is planned. For time to event analyses, patients who have no efficacy evaluations for disease recurrence will be considered censored at time 0.

For AEs, missing dates will not be imputed, however, if partial dates are available, they will be used to assess if the AE occurred during the treatment period. Missing severities of AEs will not be imputed and will be considered missing in any tabulations of AE severity. If an AE is missing a response to the question regarding relationship to treatment, the event will be considered to be related.

8.4.2 Demographics and Baseline Characteristics

The demographic characteristics to be summarized will include gender, race, ethnicity (Hispanic origin), and age at time of consent. For gender, race, and Hispanic origin, the summary statistics will be the number and percentage of patients within each group or the total sample. The categories for race will be those recorded in the database. For age at time of consent, the mean, median, minimum, maximum, and standard deviation will be provided for each group and the total sample.

Baseline characteristics include: ECOG performance status; duration from initial diagnosis; response to previous therapy (Y/N).

8.4.3 Efficacy Evaluation

Primary analysis disease control rate.

The analysis of disease control rate will be performed for each study cohort by calculating the point estimate of the percentage of patients in that cohort who have CR, PR, or SD for at least 12 weeks, assessed according to RECIST 1.1.

Duration of SD will be calculated as follows:

- For patients with documented disease progression, duration will be calculated from the date of start of study therapy until the date of disease progression.
- For patients without documented disease progression, duration will be calculated from the date of start of study therapy until the date of last disease assessment.

-
- For patients without at least one post baseline disease assessment, duration will be censored at time 0.

To be consistent with a Simon's two-stage optimal design, a lower one-sided 90% CI will be presented for the DCR in each study cohort; additionally, for descriptive purposes a two-sided 95% CI will also be calculated for each cohort, using exact methods. The DCR for each cohort will be presented for the first stage of the study and for both stages combined, consistent with the Simon's two-stage optimal design.

The analysis of differences in DCR for the randomized part of the study (Part 2) will be performed using Fisher's Exact test, accompanied by confidence intervals.

The analysis of duration of disease control will be based on the Kaplan-Meier method for estimation of summary statistics, and will include the 25th, 50th (median), and 75th percentiles and associated 95% CIs.

Secondary Analyses:

1. *Response to therapy per RECIST 1.1*: response for patients in each cohort will be determined by ORR, defined as either CR or PR using RECIST 1.1, calculated as a proportion and including a two-sided 95% CI for that cohort. Duration of response (DOR) will also be calculated; from the date of first documented occurrence of response (CR or PR) until the date of documented progression, or last disease assessment, should progression not have occurred. The analysis of DOR will be based on the Kaplan-Meier method for estimation of summary statistics, and include the 25th, 50th (median), and 75th percentiles and associated 95% CIs.
2. *Response to therapy per GCIG response criteria (RECIST 1.1 and CA-125)*: response for patients in the ovarian cohort will also be assessed for DCR and ORR, as described above, using the GCIG response criteria. Only patients with sufficient data to be assessed based on this criteria (i.e., has a baseline CA-125 assessment) will be included. Number and frequency of patients in the ovarian cancer cohort who can be assessed using the GCIG response criteria will be presented.
3. *Median Progression-free Survival*: PFS for patients in each cohort will be calculated from the date of start of study therapy to the date of progression based on RECIST 1.1, or date of death should progression not have occurred. Patients who drop out prior to study end or do not have documented PD will be censored at the day of last documented disease assessment. The analysis of PFS for patients in each cohort will be based on the Kaplan-Meier method for estimation of summary statistics, and include the 25th, 50th (median), and 75th percentiles and associated 95% CIs. PFS will also be presented with progression defined per GCIG response criteria (RECIST 1.1 and CA-125) for patients in the ovarian cohort with sufficient data to be assessed based on this criteria (i.e., has a baseline CA-125 assessment).
4. *Overall Survival*: OS for patients in each cohort will be calculated from the date of start of study therapy to the date of death due to any cause. OS rate at 12 and 24 months will also be calculated. Patients who drop out prior to study end will be censored at the day they were last known to be alive. The analysis of OS for patients in each cohort will be based on the Kaplan-Meier method for estimation of

summary statistics, and include the 25th, 50th (median), and 75th percentiles and associated 95% CIs.

5. *Quality of Life (QoL)*: will be evaluated for patients in each cohort, and for all study patients combined by EORTC QLQ-C30 after 6 and 12 weeks of treatment and approximately every 8 weeks thereafter.

